## 5. Sub Study Procedures N/A

### 6. Inclusion Criteria

- Age: > or = 18 years old
- Rotator Cuff Tendinitis
- Atraumatic Rotator Cuff Tear
- Rotator Cuff Tear Arthropathy
- Subjects who speak English

### 7. Exclusion Criteria

- Age: < 18 years old
- Prior Shoulder Surgery
- Fracture
- Acute Traumatic Rotator Cuff Tear
- Infection
- Uncontrolled Diabetes Mellitus (HbA1c >8)
- Recent Prior Shoulder Injection in either the Subacromial space
- Workers Compensation

- History of Gastric Ulcers
- Tumor Involving the Shoulder Region
- Prior history of gastrointestinal bleeding, allergic reactions, impaired renal function, seizures or cardiac arrhythmias
- Subject unable to provide informed consent
- Subjects who don't speak English
- Patients who are pregnant or lactating at time of screening or are of child bearing age
- Patients currently receiving an aspirin, NSAID regimen or any other anti-inflammatory agents that could affect inflammation response.
- Patients with any bleeding disorders.
- Patients with severe renal failure.
- Patients likely to have severe problems maintaining follow-up, including patients diagnosed with severe psychiatric conditions, patients who live too far outside the hospital's catchment area, patients who are incarcerated and patients who have unstable housing situations.
- Patients who are allergic to aspirin, ketorolac tromethamine and other NSAIDs

Spanish-speaking patients will not be enrolled at this time as the study does not have the resource and it could increase risk to participants from communication barrier. No washout period. The use of oral NSAIDS will not have any influence on the injection response. Female subjects of child-bearing age will not be enrolled into the study. Documentation of female subjects having been permanently sterilized or postmenopausal will be recorded in their medical record.

## **8. Sources of Research Material**

8.1 Information will be obtained from the subjects medical records as well as patient surveys.

8.2. Information will be obtained specifically for research purposes.

## **9. RECRUITMENT METHODS and CONSENTING PROCESS:**

### *9.1 Screening*

The treating physicians will identify potentially eligible subjects from the UT Southwestern Ambulatory Outpatient Orthopaedic Surgery clinic and John Hopkins clinics: Johns Hopkins Orthopaedics, Johns Hopkins Community Physicians, and Southern Maryland Orthopaedic and Sports Medicine Division of Centers for Advanced Orthopaedics. Study Investigators and their research teams will assess subjects for the study and include a review of the medical record to ensure none of the study exclusion criteria are met. The study will be discussed with potentially eligible subjects.

*9.2 Recruitment:* Only those presenting for a shoulder evaluation at the UT Southwestern Ambulatory Outpatient Orthopaedic Surgery clinic and John Hopkins clinics: Johns Hopkins Orthopaedics, Johns Hopkins Community Physicians, and Southern Maryland Orthopaedic and Sports Medicine Division of Centers for Advanced Orthopaedics, who meet inclusion criteria will be recruited for potential participation in the study.

Informed consent will be obtained prior to initiation of the study. The physician will be involved in the consent conversation. The conversation will be initiated by the research team and physician together. The consent process will involve a dialogue. Specifically, patients and their families will be provided with a pamphlet describing the study, the risks and benefits of participation and what will be expected of them if they choose to participate.

Consent must be obtained from the patient in this study; no legally authorized representatives or surrogates may consent on behalf of the patient. This is due to the subjective nature of assessing pain. All recruitment materials will be provided in English.

9.3 Screening, enrollment, and informed consent process will take place in a private treatment area.

9.4 If a patient decides to withdraw from the study, he/she may do so at any point by informing the Principal Investigator in writing. A 'Note to File' must be inserted into the patient's chart and research file stating the patient formally withdrew from the study with the reason (if given). The patient will be assured that the medical care which they receive will not be affected should they elect to discontinue participation in the study.

**Undue Influence:** Patients will be told they are not required to participate in research to be treated at UT Southwestern Medical Center and its affiliates or at John Hopkins clinics.

9.5 Waiver of Informed Consent: N/A

9.6 Inclusion of Vulnerable Populations: N/A

## **10. Potential Risks**

10.1 The risks associated with this study primarily concern adverse reactions to the study drugs. The drugs used in this study are not narcotics or habit-forming but can have side effects. The treating physician will screen for any heart, intestinal, or kidney disease or condition that would increase the chance for the patient to have an unwanted side effect. However, there is a small possibility that an injection of these medicines can be painful and cause bleeding or infection. The patient should seek medical assistance if any of the following occur:

- chest pain, weakness, shortness of breath, slurred speech, problems with vision or balance;
- black, bloody, or tarry stools;
- coughing up blood or vomit that looks like coffee grounds;
- swelling or rapid weight gain;
- urinating less than usual or not at all;
- nausea, stomach pain, low fever, loss of appetite, dark urine, clay-colored stools, jaundice (yellowing of the skin or eyes);
- fever, sore throat, and headache with a severe blistering, peeling, and red skin rash;
- the first sign of any mouth sores or skin rash, no matter how mild;
- pale skin, easy bruising, severe tingling, numbness, pain, muscle weakness; or
- fever, headache, neck stiffness, chills, increased sensitivity to light, purple spots on the skin, and/or seizure (convulsions).
- gastritis or gastric ulceration, intestinal bleeding, impaired renal function seizures, or irregular heartbeat.

The patient will be told to seek immediate medical help if there is any sign of an allergic reaction such as hives; difficulty breathing; or swelling to their face, lips, tongue, or throat

**Side Effects of Ketorolac.** Concerns about renal impairment, gastrointestinal irritation, and platelet inhibition constrain usage and limit the dose and duration of ketorolac administration. More directly relevant to orthopaedics, in animal models, NSAIDs in general and ketorolac in particular are known to impair osteogenesis.[28-30] The effects for these drugs, however, are reversible after short-term treatment.[28] Similarly, animal studies with chronic ketorolac administration raise concern with respect to the strength of healed wounds, with variable results for muscle and ligamentous injury.[31-33] In human studies of spinal fusion, 48 hours of ketorolac therapy for a total dose of 240 mg appears not to affect the fusion rate,[34, 35] but longer duration therapy, even at lower doses may be problematic.[36, 37] However, in a fracture model with young mice, a variety of COX antagonists did not affect long-term tibial healing,[38] consistent with a similar observation in young patients undergoing scoliosis surgery.[34]

10.3 The possibility of risks are low and will be minimized by information the patient provided from the initial questionnaire. In addition, any medicine the patient is currently taking will be evaluated by the physician to

screen for any unwanted side effects. Patients in the study will be actively monitored for any adverse reactions. The risks associated with this study primarily concern adverse reactions to the study drugs. The drugs used in this study are not narcotics or habit-forming but can have side effects. The patient's physician will screen for any heart, intestinal, or kidney disease or condition that would increase the chance for the patient to have an unwanted side effect.

## **11 Subject Safety and Data Monitoring**

The DSMB will monitor and report adverse events to ensure patient safety. Definitions and procedures for reporting adverse events are designed to satisfy 45 CFR Part 46, Subpart A; the "Common Rule", shared by 17 Departments and Agencies as well as 21 CFR 312, the FDA regulation for adverse events. The Common Rule requires written procedures and policies for ensuring reporting of "unanticipated problems" involving risks to participants to IRBs, appropriate institutional officials, and the Department or Agency Head.

11.1 We have set up a Data and Safety Monitoring Board (DSMB) with three committee members to ensure the patient's safety, one of which is not from the Department of Orthopaedic surgery. The DSMB committee will meet at least every six months or every 20 subjects to ensure that there is not more than a 5% increase in adverse events in the experimental group (ketorolac). The exhaustive list of exclusion criteria that have been put in place greatly reduce the risk of any kind of adverse or unintended consequence of the injection

11.2 Generally the DSMB would be involved in the decision of unblinding to limit potential bias. However, if a subject has a life threatening reaction to the injection, the physician is allowed to unblind the subject, without DSMB approval, to provide proper care. Immediately afterwards, the physician must report the unblinding to the study statistician and submit a detailed report explaining the unblinding event. "If unblinding occurs, the statistician should record and maintain the following in a confidential log:[39]

- ID number of the participant whose treatment assignment was unblinded
- Date
- Reason for unblinding study staff
- Person responsible for unblinding study staff
- List of persons who are unblinded.

### *Adverse event*

Any untoward or unfavorable medical occurrence in a human subject, including abnormal sign (e.g., abnormal physical exam or laboratory finding), symptom or disease temporally associated with the subject's participation in the study, whether or not considered related to the subject's participation.

### *Unanticipated problem*

Any incident, experience, or outcome that meets all of the following criteria:

- (1) is unexpected, in terms of nature, severity, or frequency, given the research procedures that are described in the protocol and informed consent document and the characteristics of the patients eligible for the study.
- (2) is related or possibly related to treatment/procedures under study; possibly related means there is a reasonable possibility that the incident, experience, or outcome may have been caused by the study procedures or treatments.
- (3) suggests that the participation in the study may place subjects or others at a greater risk of harm (including physical, psychological, economic, or social harm) than was previously known or recognized.

Please note that not all adverse events are unanticipated problems and only some unanticipated problems are in fact adverse events. For instance, if a laptop containing study data is stolen, this is an unanticipated problem but it is not an adverse event since it is not an untoward or unfavorable medical occurrence in a human subject

### ***Serious Adverse Event***

An adverse event or suspected adverse reaction is considered “serious” if, in the view of either the investigator or sponsor, it results in any of the following outcomes: Death, a life-threatening adverse event, inpatient hospitalization or prolongation of existing hospitalization, a persistent or significant incapacity or substantial disruption of the ability to conduct normal life functions, or a congenital anomaly/birth defect. Important medical events that may not result in death, be life-threatening, or require hospitalization may be considered serious when, based upon appropriate medical judgment, they may jeopardize the patient or subject and may require medical or surgical intervention to prevent one of the outcomes listed in this definition. Examples of such medical events include allergic bronchospasm requiring intensive treatment in an emergency room or at home, blood dyscrasias or convulsions that do not result in inpatient hospitalization, or the development of drug dependency or drug abuse.

- Death
- Life-threatening
- Hospitalization (initial or prolonged)
- Disability or Permanent Damage
- Congenital Anomaly/Birth Defect
- Required Intervention to Prevent Permanent Impairment
- Other Serious (Important Medical Events)

### ***Methods and Timing of Assessment***

Adverse events and complications will be assessed during the initial study visit and at follow-up phone calls and visits, as well as during any unscheduled visits to the clinic. The events will be recorded on study data forms, with a determination of whether or not they are thought to be associated with the study or with one of the study treatments.

### ***Management of Adverse Events***

Adverse Events and Serious Adverse Events will be managed according to protocol guidelines. If specific guidelines do not exist, AEs/SAEs will be managed according to the medical judgment of the treating physician.

### ***Non-Reportable Adverse Events***

Adverse events collected as study outcomes such as, somnolence, dizziness, headaches, and other central nervous system effects, peripheral edema, visual changes, dry mouth, excessive bleeding and thrombocytopenia will be recorded on study data forms whether or not they are thought to be associated with the study or with one of the treatments.

All SAEs related to use of study medications will be reported to the individual manufacturers to contribute safety data for these drugs, as well as to the FDA via the Med Watch voluntary reporting mechanism using form FDA 3500.

### ***Type and Duration of the Follow-up of Participants After Adverse Events***

Study patients who experience a SAE will be followed until resolution of the event, and a final report will be submitted to the IRB, DSMB, and FDA.

### ***Modifications of Study Agent(s)/Intervention(s) for a Participant***

#### ***Stopping Rules for an Individual Participant/Cohort***

The DSMB will review the overall progress of the trial in terms of recruitment and data quality and make a formal recommendation to the IRB at the end of each scheduled meeting as to whether the trial should continue unmodified, continue with protocol modifications or be stopped.

### ***Premature Withdrawal of a Participant***

A participant may be withdrawn from the study without consent if the investigator decides to end the study. Other reasons for removing a participant without consent may include but are not limited to non-adherence with the protocol and/or therapy, inappropriate behavior towards study personnel, etc.

## **12 Procedures to Maintain Confidentiality:**

12.1 Collected data will be maintained by an authorized member of the Orthopaedic Research Staff, Research Coordinator, or Research Nurse. All data will be kept in locked files and/or password protected electronic files, and will be used for research purposes only. No patient information will be disclosed outside the study team.

Each patient's identity and information will be collected and analyzed and will be treated with professional standards as defined by the HIPAA Compliance mandate. In addition, all requirements for HIPAA compliance concerning patient confidentiality will be adhered to. All funding agencies, Institutional Review Boards of involved centers and the U.S. Department of Health and Human Services will have the right to inspect all medical records related to this study for the purpose of verifying data and patient confidentiality. The information obtained in this study may be published in medical journals in a deidentified manner.

All hard copies of questionnaires or case report forms will be stored in the Department of Orthopaedic Surgery research office which is a key-accessed suite. Electronic records (computer files, electronic databases, etc.) is also secured and backed-up at this location.

12.2 Clinical information will not be released without written permission of the patient, except as necessary for monitoring by the IRB, FDA, or DSMB. Consent procedures and forms, and the communication, transmission and storage of patient data will comply with IRB requirements for compliance with The Health Insurance Portability and Accountability Act (HIPPA).

12.3 A Certificate of Confidentiality will not be requested for this study.

## **13. Potential Benefits**

This clinical investigation will evaluate the effectiveness of different injectable medications in controlling shoulder pain. All subjects will receive a short-term pain relief medication. This study presents possible benefits of improved pain management for subjects who are randomized to one of the treatment arms of the study. While, the researchers cannot guarantee that subjects will benefit from participation in this research directly, the subjects may benefit altruistically. The feedback provided by the subjects will assist the medical community in providing the right type of medicine for shoulder pain. Our hope is that the information learned from this study will benefit others with shoulder pain in the future. Information gained from this research could lead to better treatment for a variety of shoulder injuries.

### *Therapeutic Alternatives*

There are medical and therapeutic alternative to this study including oral medications, usual medical advice, and prescription of physical therapist. All subjects of this study will be offered these interventions at the discretion of the physician.

## **14. Biostatistics**

14.1 Statistical Analysis: The specific purpose of this study is to provide descriptive statistics for both the primary and secondary outcomes. Unpaired t or chi-square tests on all pre-op demographic data. The dependent variables will be analyzed by repeated measure of variance to determine if statistically significant differences exist at follow-up assessment. To protect against Type I error, Tukey tests will be used to ensure the alpha levels ( $p < 0.05$ ) will not be falsely declared significant. This is a prospective double-blinded randomized trial. The investigator of the study and examiner who provides the injection will be blind to which group assignment has been provided. Patients will not be told of the injection type. The billing department will create a study account which will allow billing subjects, for the ketorolac or kenalog, without their knowing which injection they received.

14.2 Sample Size: We are planning a study of a continuous response variable from independent control and experimental subjects with 1 control(s) per experimental subject. In a previous study the response within each subject group was normally distributed with standard deviation 23. If the true difference in the experimental and control means is 12, we will need to study 59 experimental subjects and 59 control subjects to be able to reject the null hypothesis that the population means of the experimental and control groups are equal with probability (power) 0.8 for each diagnostic category of rotator cuff tendinopathy, small to medium rotator cuff tears, and large rotator cuff tear arthropathies. The Type I error probability associated with this test of this null hypothesis is 0.05. To account for a 15% drop out rate we will recruit 66 subjects for each of the 3 arms of the trial in each of the 2 diagnostic categories for a total of 400 patients.

Randomization: Subjects will be recruited from the UT Southwestern Orthopaedic Surgery Clinic and John Hopkins clinics: Johns Hopkins Orthopaedics, Johns Hopkins Community Physicians, and Southern Maryland Orthopaedic and Sports Medicine Division of Centers for Advanced Orthopaedics, from patients who meet the inclusion criteria. As this study design will be prospective randomized double-blinded, we will utilize computer generated block randomization technique. After identifying a patient who meets the inclusion criteria by history, physical examination, and obtaining informed consent, HIPPA, health screen, and baseline measurements, subjects will be randomized into one of three cohorts: 1) Control (Marcaine injection), 2) NSAID injection (ketorolac & Marcaine injection), or 3) Steroid injection (kenalog & Marcaine injection). To ensure that the number of subjects is about the same in the three arms of the study, the randomization scheme will assign patients in a 1:1:1 ratio in randomly permuted blocks of assignments stratified by clinical center. Block size will be determined randomly and the patient will be the unit of randomization.

Enrollment and randomization results will be documented in the patient's chart according to protocol. The randomization allocation will be blinded to both the patient (initially) as well as the physician performing the injection and the investigator conducting statistical analysis of the results. Given the nature of this study looking at the effects of this intervention on multiple shoulder pathologies we anticipate approximately 200 subjects per diagnostic category would be needed for enrollment and complete follow-up.

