### **3. Concise Summary of Project**

**3.1 Study Design:** The proposed study is a three arm, double-blinded, prospective randomized controlled clinical trial with follow-up immediately after the injection and at day 2, and weeks 1, 2, 4, 6, and 12. In this study we will compare the effectiveness of ketorolac compared to corticosteroid.

Ketorolac is an injectable solution which should be stored at 15 C to 30 C (59 F to 86 F) and protected from light. Marcaine (Bupivacaine) should be stored at room temperature, between 20 C to 25 C (68 F to 77 F). And Kenalog (triamcinolone) should be stored at controlled room temperature, 20°–25°C (68°–77°F), avoid freezing and protect from light. Do not refrigerate.[18]

Medications are stored in a locked cabinet at room temperature. The Research Team will prepare the appropriate injection medication according to group assignment at the time of the appointment. Injections will not be prepared beforehand. Injections will be prepared by inserting the syringe into both bottles and drawing the required amount. The syringe contents will be masked from the physician.

**Study Groups:** Subjects being seen for a rotator cuff injury will be randomized into one of three treatment groups pertaining to their pathology. The intervention will begin once the subject has consented and answered the Baseline Outcome Shoulder Questionnaire. The Baseline Outcome Questionnaire consists of the Visual Analog Score, American Shoulder and Elbow Score, Single Assessment Numeric Evaluation, Pittsburgh Sleep Quality Index, SF-12, range of motion and measure the subjects shoulder strength by using a

dynamometer, and questions pertaining to patient characteristics, injury characteristics, co-morbidities, patient history, medications, and demographics.

A dynamometer is a small, hand-held device which the subject presses against. By pressing against the device, it measures the strength of their shoulder.

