#### *Follow-up Interviews*

Subjects will be contacted by phone to obtain VAS score at day 2, and weeks, 1, 2, and 4 after the injection. They will be instructed to return to clinic at routine follow-up intervals at 6 and 12 weeks after the injection and will again be asked to complete the Outcome Shoulder Questionnaire containing VAS, ASES, SF-12, PSQI scores. Subjects range of motion and shoulder strength will also be collected. All data collected with regards to this study will be kept in a password-protected database, which will only be accessible, by study investigators and the research team.

Study subjects who do not respond to the follow-up phone calls in a timely manner, will be mailed a paper copy of the Follow-up Outcome Shoulder Questionnaire and/or emailed a website link to the same questionnaire on [www.surveymonkey.com](http://www.surveymonkey.com)

	Baseline Shoulder Questionnaire			Follow-up					
	Med Record Review	Pre-Injection	5 Minutes Post Injection	Day 2	Week 1	Week 2	Week 4	Week 6	Week 12
Visual Analog Score (VAS)		X	X	X	X	X	X	X	X
American Shoulder and Elbow Score (ASES)		X						X	X
Single Assessment Numeric Evaluation (SANE)		X	X					X	X

Pittsburgh Sleep Quality Index		X					X	X
SF-12		X					X	X
Range of Motion		X	X				X	X
Dynamometer measurements		X	X				X	X
Pt Characteristics	X							
Injury Characteristics	X							
Co-Morbidities	X							
Pt Hx	X							
Meds	X							
Demographics	X							

4.3 Each phone follow-up should take approximately 10 minutes each and the standard follow-up visits should each take approximately 30 to 45 minutes.

4.4 At each time frame, the subjects will be asked to complete a questionnaire. Blood and tissue samples will not be collected for this study.

4.5 Subjects will be billed for the services received whether they participate in the study or not.

4.6 The only change in clinic practice of shoulder disorders as part of this study protocol will be the randomization of injection medication they will be receiving. Subjects will be prescribed physical therapy as is standard for the treatment of shoulder disorders.

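### Section 14.1 does not specify adjustment for the pre-injection VAS and ASES scores that the trial already collects, and so gives up precision that would need no new data

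*Combined protocol and SAP*

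**What the plan says.** The efficacy analysis in Section 14.1 consists of two statements. The model is: "The dependent variables will be analyzed by repeated measure of variance to determine if statistically significant differences exist at follow-up assessment". The multiplicity rule is: "To protect against Type I error, Tukey tests will be used", at a level of 0.05. No covariate is named. The only use of pre-treatment data that the section describes is t or chi-square tests on demographics.

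The baseline scores exist. Under Study Groups in Section 3.1: "The Baseline Outcome Questionnaire consists of the Visual Analog Score, American Shoulder and Elbow Score", followed by the other instruments. The visit schedule in Section 4 marks VAS and ASES before the injection. Follow-up VAS is planned at 5 minutes, day 2 and weeks 1, 2, 4, 6 and 12; follow-up ASES is planned at weeks 6 and 12.

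Section 14.2 sizes a two-group comparison of means with difference 12, SD 23, type I error 0.05 and power 0.8, which gives 59 per group. It recruits 66 per arm for the "3 arms of the trial in each of the 2 diagnostic categories", allowing for 15% dropout. The Randomization paragraph describes "randomly permuted blocks of assignments stratified by clinical center".

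**The concern.** A pain or function score before treatment usually predicts the same score afterwards. A model that uses it removes part of the between-subject variation from the arm comparison. Section 14.1 does not say how, or whether, baseline enters, and two readings are open:

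- Baseline is left out, and the arms are compared on follow-up values alone.
- Baseline is one level of the time factor, and the treatment effect is read as a difference in change.

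Neither is the efficient choice, and the second can be clearly worse than the first when the correlation is low. At stake are wider intervals and less power for the three pairwise arm contrasts than the same subjects and data could give. Because the model is left open, the choice could also be made after results are seen.

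**Working it through.** **Inputs.** Difference 12, SD 23, 0.05, 66 per arm and 15% dropout come from Section 14.2. Evaluable per arm within a diagnostic category: 66 × 0.85 = 56.1, taken as 56. The documents give no baseline-outcome correlation r, so values from 0.2 to 0.6 are assumed. Section 14.2 does not say whether 23 is the SD of a follow-up value or of a change, so both are tried. Equal SDs at baseline and follow-up are assumed.

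**Step 1: reproduce the plan's figure.** Two-sided two-sample t test, noncentrality 12 / (23 × √(2/n)). At n = 59 this is 2.83 and power is 0.802; at n = 58 power is 0.796. The stated 59 is therefore an unadjusted two-group calculation. At n = 56 the same test has power 0.78.

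**Step 2: direction of the gain.** Relative to the follow-up variance, the variance of the arm comparison at one visit is proportional to:

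- baseline ignored: 1
- change contrast: 2(1 − r)
- baseline as covariate: 1 − r²

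For 0 < r < 1, 1 − r² is below 1. It is also below 2(1 − r), because 1 − r² = (1 − r)(1 + r) and 1 + r < 2. So the covariate is more precise under either reading of 14.1. The covariate costs one degree of freedom, which is negligible here.

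**Step 3: size, with 23 as a follow-up SD.** The Tukey critical value is the 95% studentized range for three arms divided by √2, with 3 × 56 − 3 = 165 degrees of freedom: 2.365. With baseline ignored, noncentrality is 12 / (23 × √(2/56)) = 2.76 and power is 0.65. For the other two models:

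| r | SD, change: 23√(2(1 − r)) | Power, change | SD, covariate: 23√(1 − r²) | Power, covariate |
|---|---|---|---|---|
| 0.2 | 29.09 | 0.43 | 22.54 | 0.67 |
| 0.3 | 27.21 | 0.49 | 21.94 | 0.70 |
| 0.5 | 23.00 | 0.65 | 19.92 | 0.79 |
| 0.6 | 20.57 | 0.76 | 18.40 | 0.86 |

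The simultaneous 95% half-width is 2.365 × SD × √(2/56). It is 10.3 points with baseline ignored. At r = 0.3/0.5/0.6 it is 12.2/10.3/9.2 for change and 9.8/8.9/8.2 with the covariate.

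**Step 4: size, with 23 as a change SD.** The follow-up SD is then 23 / √(2(1− r)), and the covariate-adjusted SD is that value times √(1 − r²).

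| r | Power, ignored | Power, change | Power, covariate |
|---|---|---|---|
| 0.3 | 0.82 | 0.65 | 0.85 |
| 0.5 | 0.65 | 0.65 | 0.79 |
| 0.6 | 0.54 | 0.65 | 0.76 |

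The covariate is still best in every row, but the low change-contrast figures of Step 3 no longer apply.

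**Step 5: does it depend on reading a single visit?** For the mean of m visits with equal correlations, the variance factors are (1 + (m − 1)r)/m with baseline ignored, that plus 1 − 2r for change, and that minus r² with the covariate. For the two clinic visits (m = 2) at r = 0.3/0.5/0.7, the covariate variance is 0.86/0.67/0.42 of the ignored-baseline variance and 0.53/0.67/0.80 of the change variance. The direction is the same.

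**The case against.** **Silence is not refusal.** Section 14.1 names a family of methods and excludes no covariate. This stands: the supportable statement is that adjustment is not specified.

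**Nothing is invalid.** The unadjusted comparison of randomized arms is valid, and Section 14.2 was sized for one, so the plan is consistent with itself on this point. This also stands. A reader might infer from 0.65 that the stated 0.80 is wrong. That does not follow: 14.2 concerns a single two-group test at 0.05, whereas 0.65 uses a three-arm Tukey criterion at 56 per arm.

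**The size rests on assumptions.** The correlation is not in the documents. With 23 as a follow-up SD, Tukey power rises only from 0.65 to 0.66 at r = 0.1 and to 0.67 at r = 0.2. The status of the SD is also unstated. Both points limit the size of the gain but not its direction.

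**One visit is not the whole plan.** A repeated-measures main effect averages over visits and would have more power than a single-visit contrast. That is fair, and 14.1 does not say which contrast is read. The single-visit figures illustrate the difference between models and are not the power of the trial.

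**Missed visits.** A reader might also infer that the analysis will drop anyone who misses one of the VAS follow-ups, with loss of power or bias. The documents do not support this. Section 14.1 states no complete-row rule, and the Follow-up Interviews paragraph provides mailed or emailed questionnaires for subjects who do not respond by phone.

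**Conclusion.** The point holds as a recommendation: 14.1 should specify the pre-injection score as a covariate. The direction of the gain is algebraic and does not depend on which reading of 14.1 is intended. Its size does depend on assumptions. If 23 is a follow-up SD, single-visit Tukey power improves over ignoring baseline by 0.02 at r = 0.2 and by 0.21 at r = 0.6. Over a change contrast it improves by 0.24 at r = 0.2 and by 0.10 at r = 0.6. If 23 is a change SD, the improvement over ignoring baseline runs from 0.03 at r = 0.3 to 0.22 at r = 0.6. Over the change contrast it runs from 0.20 down to 0.11 across the same range. The matter is one of efficiency and of fixing the model in advance; it gives no ground for calling the planned comparison biased.

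**What to change.** In 14.1, replace the model sentence with a mixed model on the post-injection visits: day 2 to week 12 for VAS, and weeks 6 and 12 for ASES. Include treatment, visit, treatment-by-visit, the pre-injection score of the same outcome as covariate, and clinical centre as the stratification factor. The centre term adds only a small further gain. Keep the Tukey adjustment for the three pairwise arm contrasts, read at a visit that 14.1 names.

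Define baseline as the pre-injection value. Treat the 5-minute VAS as a post-treatment measurement, never as baseline. When this is written, also state in 14.2 which scale the SD of 23 belongs to and whether it is a follow-up or a change SD.

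The cost is SAP wording and slightly more analysis work. Baseline scores and centre are already recorded, so no new data, visits or subjects are needed. The change should be made before unblinding.
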